**Patients who have planned surgery or planned osteotomy will not automatically be ineligible for the trial. Every potential participant with planned surgery or osteotomy will be assessed clinically on a case by case basis through discussion of the site PI^a, with the CI and/or the clinical members of the TMG during the screening process. NB: Please ensure that patients fulfil the full eligibility criteria prior to enrolling them on to the trial and ensure eligibility is re-assessed after the baseline observation period is complete, and before the participant begins treatment with CBZ. If a patient is deemed unsuitable at the end of the baseline observation period re-assessment time point, further reassessment of eligibility is possible if the Site PI^a and CI are in agreement that the exclusionary results are subject to change. In such cases, eligibility can be re-assessed within a 3 month period. If a patient meets any of the exclusion criteria after the 3 month reassessment period, they will be withdrawn from the study.

Protocol waivers will not be permitted for this trial. Enrolling a patient who does not meet the inclusion/exclusion criteria is considered a protocol waiver and is in breach of Regulation 29 (SI 2004/1031) of the Medicines for Human Use (Clinical Trials) Regulations 2004 and EU Clinical Trial Directive 2001.

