**Visit 1.1 may coincide with baseline observation visit 3 (Table 5). If visit 1.1 does not coincide with baseline observational visit 3, it must be within 14 days of baseline observation visit 3. Visit 1.6 may coincide with stage 1 treatment visit 2.1.

*** Adhoc safety visit to be performed if clinically indicated

***** Pregnancy testing will only be performed if deemed necessary by clinical team

****** A maximum of 2ml blood will be taken for exploratory biomarker analysis and a maximum of 2ml blood will be taken for the measurement of Bone markers (osteocalcine and CTX), if available at site.

% As this is a paediatric population, if there are difficulties in drawing blood or enough blood cannot be collected and to prevent multiple draws in one visit, it will be discussed with the PI^a and the CI whether there is a clinical need to bring the participant back into clinic in the next 14 days for another blood draw attempt.

2018-002633-38

Table 7 – Schedule of events - Stage 1,	Treatment phase (UK participants only)
---	--

Assessment*	Visit 2.1** 0 months (+/- 14 days)	Weekly Telephone call (as required)****	Visit 2.2 3 months (+/- 14 days)	Visit 2.3 6 months (+/- 14 days)	Visit 2.4 9 months (+/- 14 days)	Visit 2.5 12 months (+/- 14 days)	Visit 2.6 15 months (+/- 14 days) [△]	Visit 2.7 18 months (+/- 14 days) [△]	Visit 2.8 21 months (+/- 14 days) ^{∆ ∞}	Visit 2.9 24 months (must be completed on/before 31/01/2024) ^A
Informed consent/assent						Χα				
Eligibility check	Х					Χα				
Physical examination	Х		Х	Х	Х	Х	Х	Х	Х	X
Confirmation of eligibility	Х									
Tanner stage	Х		Х	Х	Х	Х	Х	Х	Х	X
Growth measurements	Х		Х	Х	Х	Х	Х	Х	Х	X
X-rays (left wrist for bone age and long leg standing AP)	X			x		x		Х		x
Laboratory safety assessments (including urine dipstick) %	x			x		x		х		х
Bone biochemistry %	Х			Х		Х		х		X
Pregnancy testing (potentially child bearing females only)	x		x	x	x	x	x	х	х	x
EQ-5D-Y questionnaire	Х		Х	Х	Х	Х	Х	х	Х	X
PEDSQL questionnaires (QoL Inventory, Pain coping Inventory & Pain Questionnaire)	x		х	x	x	x	х	х	х	х
Dose Evaluation		X								
Drug prescription	Х		Х	Х	Х	Х	Х	Х	X☆	
Adverse event recording	Х	X	Х	X	Х	X	Х	Х	Х	X
Medication counselling	X	X	X	X	X	X	X	X	Х	X
Concomitant medications	Х	X	Х	X	X	X	Х	X	Х	X
Biomarker blood sample (UK participants only)*****	X		X	X	X	X	X	X	X	x

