Adverse event recording			X	X
Concomitant medications	X		X	X
Biomarker blood sample (UK participants only)***			x	x

--Informed consent is ongoing process, if a participant moves age groups during the trial, the age appropriate PIS will be provided, and the participant will be re-consented *All assessments to be performed as described in the protocol trial assessments section 8.7

**Screening visit 1 and 2 may coincide with baseline observation visit 1 and baseline observation visit 2 may coincide with treatment visit 2.1 (Table 9) for stage 2 participants.

*** A maximum of 2ml blood will be taken for exploratory biomarker analysis and a maximum of 2ml blood will be taken for the measurement of Bone markers (osteocalcine and CTX), if available at site.

Assessment*	Visit 2.1** 0 months (+/- 14 days)	Weekly Telephone call (as required)****	Visit 2.2 3 months (+/- 14 days)	Visit 2.3 6 months (+/- 14 days)	Visit 2.4 9 months (+/- 14 days) ∞	Visit 2.5 12 months (must be completed on/before 31/01/2024)
Eligibility check	X					
Physical examination	X		Х	Х	X	Х
Confirmation of eligibility	x					
Tanner stage	X		X	X	Х	Х
Growth measurements	X		x	X	Х	Х
X-rays (left wrist for bone age and long leg standing AP)	x			x		х
Laboratory safety assessments (including urine dipstick) %	x			x		x
Bone biochemistry %	X			Х		X
Pregnancy testing (potentially child bearing females only)	x		x	x	x	Х
EQ-5D-Y questionnaire	x		Х	Х	Х	Х
PEDSQL questionnaires (QoL Inventory, Pain coping Inventory & Pain Questionnaire)	x		x	x	x	Х
Dose Evaluation		X				
Drug prescription	X		X	Х	X≎	
Adverse event recording	X	X	X	Х	X	Х
Medication counselling	X	X	X	Х	X	Х
Concomitant medications	X	X	X	Х	X	Х
Biomarker blood sample (UK participants only)*****	x		x	x	x	х

Table 9 – Schedule of events - Stage 2, Treatment phase (UK, Europe & International sites)

* All assessments to be performed as described in the protocol trial assessments section 8.7

**Visit 2.1 may coincide with stage 2 baseline observation visit 2 (Table 8). If visit 2.1 does not coincide with baseline observational visit 2, it must be within 14 days of baseline observation visit 2

**** phone calls may be required, if patient is unable to tolerate 20mg/kg dose and requires dose titration

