2.5.1 MCDS-Therapy participant visit schedule (modified from Protocol version)

	Stage 1: Dose ti	: Dose titration participant		Stage 2: Treatment phase participants		
Stage of trial	Visit	Timepoint		Visit	Timepoint	
Consent/screening	Consent Screening visit 1*			Consent Screening visit		
and eligibility	Screening visit 2*	Up to 2 consent	8 days post	Screening visit 2*	Up to 28 days post consent	
Basalina	Visit 1*	0	Months	Visit 1*	0	Months since
observation	Visit 2	6**	since Baseline	Visit 2	6	Baseline observation
phase	Visit 3*	12***	observation			
	Visit 1.1*	0	Weeks			
	Visit 1.2	2	since start			
Dose titration	Dose evaluation telephone calls	1 -11	titration phase			
phase	Visit 1.3	3				
	Visit 1.4	6				
	Visit 1.5	9				
	Visit 1.6	12				
	Visit 2.1*	12*	Months	Visit 2.1*	0	Months
	Visit 2.2	15	since start	Visit 2.2	3	since start
Treatment phase	Visit 2.3	18	of Dose	Visit 2.3	6	of
	Visit 2.4	21	phase	Visit 2.4	9	phase
	Visit 2.5	24		Visit 2.5®	12	h
	Visit 2.6 ^Δ	27				
Optional extended	Visit 2.7 ^a	30				
treatment phase	VISIT 2.8 ⁴	33				
	VISIL 2.9	50				

*Visits which may coincide with the preceding or proceeding visit: - Screening visit 1 and 2/Visit 1 baseline observation; Visit 3 baseline observation/Visit 2.1 treatment phase

**6 month visit may be missed for participants who have experienced delays to their visit schedule due to COVID-19 halt to the trial

***12 month visit may be rescheduled to 18 month visit for participants who have missed the 12 month visit due to COVID-19

^A This is an optional visit subject to an additional informed consent

[®] Visit 2.5 in Stage 2 and visit 2.9 in Stage 1 must occur no later than 31st January 2024.

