4.3.1 Statistical model for growth

For subject *i* (*i* = 1,..,*N*), let τ_{ij} be a treatment indicator taking the value 0 for measurements observed during the baseline period and 1 for measurements observed during the treatment period; treatment for individual *i* starts at time T_i .

Let y_{ij} denote a continuous response variable (e.g., height), observed at measurement times t_{ij} (j = 1,.., n_i), the model for which is:

$$y_{ij} = \beta_1 + \beta_2 t_{ij} + \beta_3 \tau_{ij} (t_{ij} - T_i) + \varepsilon_{ij},$$

where β_1 , β_2 and β_3 are regression parameters to be estimated using Generalised Estimating Equations (GEE). The "working" correlation matrix is given by,

$$Corr(\varepsilon_{ij}, \varepsilon_{ij'}) = \begin{cases} 1 & if \ j = j' \\ \rho & otherwise \end{cases}$$

This is sometimes referred to as an exchangeable covariance model. The first observation on each individual, y_{i1} , takes place at time t_{i1} =0.

- During the baseline period, $y_{ij} = \beta_1 + \beta_2 t_{ij} + \varepsilon_{ij}$.
- At the start of the treatment period, $y_{ij} = \beta_1 + \beta_2 T_i + \varepsilon_{ij}$.
- During the treatment period, $y_{ij} = (\beta_1 \beta_3 T_i) + (\beta_2 + \beta_3)t_{ij} + \varepsilon_{ij}$.

The parameter β_3 represents the change in slope between the baseline and treatment periods, i.e., the change in growth velocity.

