4.3.2 Analysis

All patients who have completed the baseline observation period and have received at least one dose of CBZ will be included in the primary analysis.

Height measurements will be displayed graphically by individual indicating measurements taken during baseline and treatment periods.

Height measurement data will be analysed using the STATA commend **xtgee** to estimate the parameters of the regression model in 4.3.1. The parameter β_3 representing the change in growth velocity will be reported together with 95% confidence interval. The Huber/White/sandwich estimator of variance will be used to obtain confidence intervals [in STATA: vce(robust)].

If fitting the growth model in section 4.3.1 is problematic, for example, lack of convergence, then a simplified analysis will be considered.

For subject *i* (*i* = 1,..,*N*), let v_{ik} denote growth velocity (a continuous response variable) measured during the baseline period (*k*=1) and the treatment period (*k*=2). Growth velocity during the baseline period for each participant will be estimated using the first available and last available measurement during the baseline period; the growth velocity during the treatment period will be estimated in a similar manner.

The model for growth velocity is:

$$v_{ik} = \beta_1 + \beta_{2i} + \beta_3 P_k + \varepsilon_{ik},$$

where β_1 , β_{2i} and β_3 are regression parameters to be estimated using simple linear regression. P_k takes the value 0 for baseline period velocities (*k*=1) and 1 for treatment period velocities (*k*=2). As for the previous GEE model, the parameter β_3 represents the change in growth velocity between treatment and baseline periods. The parameter β_3 representing the change in growth velocity will be reported together with 95% confidence interval.

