4.4.2 Statistical modelling

A more general version of the statistical model used for the analysis of the primary outcome will be used to assess changes in secondary outcome measures possibly related to treatment. The model additionally allows for a possible step change in response at the start of the treatment period.

Defining τ_{ij} , t_{ij} and T_i in the same manner as used for the primary outcome analysis, let y_{ij} denote a continuous response variable, the model for which is:

$$y_{ij} = \beta_1 + \beta_2 t_{ij} + \beta_3 \tau_{ij} (t_{ij} - T_i) + \beta_4 \tau_{ij} + \varepsilon_{ij},$$

where β_1 , β_2 , β_3 and β_4 are regression parameters to be estimated using Generalised Estimating Equations (GEE). The "working" correlation matrix is the same as used for the primary analysis.

- During the baseline period, $y_{ij} = \beta_1 + \beta_2 t_{ij} + \varepsilon_{ij}$.
- At the start of the treatment period, $y_{ij} = \beta_1 + \beta_2 T_i + \beta_4 + \varepsilon_{ij}$.
- During the treatment period, $y_{ij} = (\beta_1 \beta_3 T_i + \beta_4) + (\beta_2 + \beta_3)t_{ij} + \varepsilon_{ij}$.

The step change in response at the start of the treatment period is modelled by the parameter β_4 ; the parameter β_3 represents the increase in slope during the treatment period compared to the baseline period as previously.

Height *zscore*, PedsQL Pain Coping Inventory total score, Pediatric Pain Questionnaire VAS score, Paediatric Quality of Life Inventory (PedsQL) total score, PedsQL Psychosocial Health sub-domain score and PedsQL Physical Health sub-domain score will be analysed using the STATA commend **xtgee** to estimate the parameters of the regression model above. The parameter β_3 and β_4 will be reported together with 95% confidence interval. The Huber/White/sandwich estimator of variance will be used to obtain confidence intervals [in STATA: vce(robust)].

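### SAP 4.4.2, read literally, codes the pre-dose month-0 value as on treatment and gives no rule for a month-0 visit shared with the last baseline visit; that coding would shrink a true early step and create a false slope change

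*SAP*

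**What the plan says.** SAP 4.3.1 defines tau_ij as a "treatment indicator taking the value 0 for measurements observed during the baseline period and 1 for measurements observed during the treatment period", with treatment of child i starting at time T_i. Section 4.4.2 takes over tau, t and T "in the same manner as used for the primary outcome analysis" and adds beta_4*tau_ij: "The step change in response at the start of the treatment period is modelled by the parameter" beta_4. Its equation for the start of the treatment period is beta_1 + beta_2*T_i + beta_4 + error. The model is fitted by GEE with exchangeable working correlation to height z-score, the pain scores and the PedsQL scores. Both beta_3 and beta_4 are reported with 95% confidence intervals.

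The SAP 2.5.1 schedule lists visit 1.1 (Stage 1) as month 0 of titration and visit 2.1 (Stage 2) as month 0 of treatment, both outside the baseline phase. In protocol Tables 6 and 9 the same visits carry the eligibility check, the questionnaires and the first prescription. Protocol 7.2 asks sites to "ensure eligibility is re-assessed after the baseline observation period is complete, and before the participant begins treatment with CBZ".

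The month-0 visit can also be the last baseline visit. The Table 6 footnote says "Visit 1.1 may coincide with baseline observation visit 3 (Table 5"), and the Table 9 footnote says "Visit 2.1 may coincide with stage 2 baseline observation visit 2 (Table 8"). Otherwise the two visits must be within 14 days of each other. Neither document says which value of tau a shared record takes, or whether it is entered once or twice.

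**The concern.** The step term is there to pick up a change that appears when carbamazepine starts. If the month-0 score is coded as treated, the model is told that a pre-treatment value already carries the effect. The fitted treatment line is then pulled toward the untreated level at its left end. The step comes out too small, and a slope change appears that is not there.

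Pain is where this could matter most, because an early change is plausible: protocol 9.1 lists neuropathic pain among the drug's licensed uses. A reader of the results could take a prompt effect for a gradual one.

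The missing rule for shared visits adds a loss of precision. A Stage 2 child has only two baseline visits, at months 0 and 6. If the second is shared and coded tau = 1, that child has one baseline value left and contributes no within-child baseline slope.

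**Working it through.** The plan gives no figure for this point, so there is none to reproduce. The check asks what the 4.4.2 model estimates when the truth is known.

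**Inputs from the documents.** Stage 1 has 11 children, with baseline visits at months 0, 6 and 12, then three-monthly visits to 24 months of treatment (optionally 36). Stage 2 has 29 children, with baseline visits at months 0 and 6, then three-monthly visits to 12 months. The working correlation is exchangeable.

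**Assumptions.** All visits are attended. The true response is a step of 1 at every visit after month 0 and 0 up to and including month 0, with no true slope change. The correlation rho is not given, so 0.3 to 0.95 is used. The share of children with shared visits is not given, so all-separate and all-shared are both run.

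**Hand check, 12 months of treatment data, tau = 1 at month 0.** All baseline values are 0, so the baseline line is 0 and beta_4 is the height of the treatment line at T_i.
- Times 0, 3, 6, 9, 12 (mean 6); values 0, 1, 1, 1, 1 (mean 0.8).
- Sxx = 36 + 9 + 0 + 9 + 36 = 90.
- Sxy = (-6)(0) + (-3)(1) + 0(1) + 3(1) + 6(1) = 6.
- False slope = 6/90 = 0.0667 per month = 0.80 of the step per year.
- beta_4 = 0.8 - 6 x 0.0667 = 0.40 of the step.

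**Same check, a child followed for 24 months.** There are nine visits (mean time 12, mean value 8/9). Sxx = 540 and Sxy = 12, so the slope is 0.0222 per month = 0.267 per year, and beta_4 = 0.889 - 0.267 = 0.622. Longer follow-up dilutes the miscoded point but does not remove the bias.

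**Pooled design.** The expected GEE coefficients are (sum X'V^-1 X)^-1 (sum X'V^-1 m). Here X has columns 1, t, tau(t - T) and tau; V = (1 - rho)I + rho J; and m is the true mean. The pooled fit is not an average of the two hand checks, because the baseline slope is common to both stages.

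| Treatment data used, tau = 1 at month 0 | beta_4 / true step | False beta_3 (steps per year) |
|---|---|---|
| First 12 months, both stages | 0.40 | 0.80 |
| Stage 1 to 24 months, visits separate | 0.56-0.58 | 0.46-0.49 |
| Stage 1 to 24 months, visits shared | 0.63-0.66 | 0.58-0.62 |
| All 11 Stage 1 children to 36 months, separate or shared | 0.68-0.74 | 0.24-0.36 |

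With tau = 0 at month 0, beta_4 = 1.00 and beta_3 = 0 in every case.

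**Precision.** With shared visits coded tau = 1, the SE of beta_4 is 1.6-2.2 times that with tau = 0 when Stage 1 runs to 24 months. Taking the 12- and 24-month windows together, the ratio is about 1.4-2.2.

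**Illustration with assumed values** (step -10 on the 0-100 pain scale, SD 25, rho 0.5, Stage 1 to 24 months; 400 simulated trials with robust SEs):
- Separate visits: mean beta_4 is -5.55 with tau = 1 and -10.02 with tau = 0. Coverage of the true -10 by the 95% interval is 67% and 95%.
- Shared visits: mean beta_4 is -6.75 and -9.96, with SE 6.04 and 3.41.

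**Primary model.** It has no step term, and tau(t - T_i) = 0 at t = T_i whatever tau is. A height at T_i therefore enters identically under either coding.

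**The case against.** The strongest reply is that no sentence assigns visit 1.1 or 2.1 a value of tau. The start-of-treatment equation can be read as the level just after T_i, which is an ordinary way to show where a step sits. That reading is open, and a reader should not infer that the SAP certainly codes a pre-dose value as treated. It does not settle the matter, though, because the coding of the visit is then simply unstated.

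Other limits also stand:
- The bias needs a real early step. With no effect, or a pure slope change from T_i, both codings are unbiased. Height z-score reflects accumulated growth, so an immediate step there is implausible. Dosing also starts at 5 mg/kg/day and rises weekly.
- No single percentage follows from the documents. The SAP frames the secondary outcomes as over 12 months but fixes no data window for the model.
- Pre-dose status is inferred from the eligibility check and first prescription at that visit. No sentence orders the questionnaire before the first dose, although questionnaires may be completed at home beforehand.
- The SAP 2.5.1 footnote "Visit 3 baseline observation/Visit 2.1 treatment phase" does not support sharing in Stage 2. Only Stage 1 has a baseline visit 3, and Stage 1 visit 2.1 falls 12 months into treatment. Sharing rests on the protocol footnotes.
- With shared visits at tau = 1, Stage 2 alone cannot identify all four parameters (rank 3). SAP 2.1 pools the stages, so the planned model can still be fitted.
- One might infer that the 4.3.2 fallback fails too, since "Growth velocity during the baseline period for each participant will be estimated using the first available and last available measurement during the baseline period". Height is scheduled under both the last baseline visit and month 0, so a shared height naturally serves as both. A sentence there would be clarification only.
- No decision rule uses beta_4, and SAP 4.4.1 plots each child's values with the periods marked.

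**Conclusion.** The concern holds as a minor point on the secondary-outcome model. Following the SAP's definitions literally puts a pre-dose value on the treatment side of the step; on the looser reading, the coding of that visit is undefined. Shared visits have no rule on either reading.

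If tau = 1 is used and there is an immediate step, beta_4 is understated: it recovers from 40% to 74% of the step, depending on how much Stage 1 follow-up enters. Part of the effect is reported as a slope change instead. The direction was the same in every case tried; the size rests on full attendance and on the assumed correlation range. The practical concern is pain and PedsQL. A reader might infer that the primary growth-velocity result is biased as well; the primary model as written rules that out.

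**What to change.** Add to SAP 4.4.2: tau_ij = 0 for every measurement taken before the first dose, including visit 1.1 (Stage 1) and visit 2.1 (Stage 2 only); tau_ij = 1 only for t_ij > T_i; a month-0 visit shared with the last baseline visit is entered once, with tau = 0. Present the second equation as the limit just after T_i, not as the model for the month-0 record.

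This needs no new data or visits. The SAP is dated 8 February 2024 and expects the final analysis in spring 2024, so the rule can be set before results are seen. With separate visits, the SE of beta_4 is about unchanged when Stage 1 runs to 24 months and about 15-19% larger with 12-month data only. With shared visits, precision improves.

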4.4.3 Additional secondary analyses

Use of surgical interventions to manage the condition will be captured on the eCRF over the whole follow up period. These will be reported descriptively as the type and proportion of participants experiencing an event per three month period from baseline until the end of trial follow up.

5 Safety

Laboratory safety assessments outside the appropriate local normal reference range will be reported at a participant level. Abnormal physical examinations will be reported at a participant level together with any further details provided.

All AEs occurring from the point of consent to the end of trial participation are recorded in the trial MACRO database eCRF. AEs are assessed for their relationship to treatment and coded as: Unrelated, Unlikely, Possible, Probable, Definitely, or Not assessable. Severity is graded according to the Common Terminology Criteria for Adverse Events (CTCAE), Version 5.0, Published: November 27, 2017.

Grading is based on the following general guideline:

- **Grade 1 Mild**; asymptomatic or mild symptoms; clinical or diagnostic observations only; intervention not indicated.
- **Grade 2 Moderate**; minimal, local, or non-invasive intervention indicated; limiting age-appropriate instrumental Activities of Daily Living (ADL).
- **Grade 3 Severe** or medically significant but not immediately life-threatening; hospitalization or prolongation of hospitalization indicated; disabling; limiting self-care ADL.
- Grade 4 Life-threatening consequences; urgent intervention indicated.
- Grade 5 Death related to AE.

AEs are coded using the Medical Dictionary for Regulatory Activities (MedDRA) version 22.0. The Clinical Data Management System (CDMS) auto-codes the majority of AEs to the latest version of the MedDRA dictionary. If this is not possible, AEs are coded from the MedDRA dictionary by the Cl.

SARs occurring from the first participant's dose of IMP to the last participant's end of follow-up are recorded on the trial MACRO database eCRF. Following this defined active monitoring period for SARs, investigators are still required to report any SARs or SUSARs which are brought to their attention.

For each SAE the following information is collected:

- 1. Full details in medical terms and case description
- 2. Event duration (start and end dates, if applicable)
- 3. Action taken
- 4. Outcome
- 5. Seriousness criteria
- 6. Causality in the opinion of the investigator
- 7. Whether the event is considered expected or unexpected in accordance with the approved RSI if a causal relationship is suspected.

